6.7. Intervention after the End of the Study

Not applicable.

7. Discontinuation of Study Intervention and Participant Discontinuation/Withdrawal

Participants discontinuing from the study prematurely for any reason must complete AE and follow-up procedures per the SoA (Section 1.3) of the protocol.

7.1. Discontinuation of Study Intervention

In rare instances, it may be necessary for a participant to permanently discontinue (definitive discontinuation) study intervention. If study intervention is definitively discontinued, the participant will remain in the study for additional data collection consistent with routine safety monitoring. See the SoA (Section 1.3) for data to be collected at the time of discontinuation of study intervention and follow-up and for any further evaluations that need to be completed.

If a clinically significant finding is identified after enrollment, the investigator or qualified designee will determine if the participant can continue in the study and if any change in participant management is needed. Any new clinically relevant finding should be reported as an AE.

See the SoA (Section 1.3) for data to be collected at the time of intervention discontinuation and follow-up and for any further evaluations that need to be completed.

7.2. Participant Discontinuation/Withdrawal from the Study

A participant may withdraw from the study:

- at any time at his/her own request
- at the request of his/her designee (for example, parents or legal guardian)
- at the discretion of the investigator for safety, behavioral, compliance, or administrative reasons
- if the participant becomes pregnant during the study
- if enrollment in any other clinical study involving a study intervention or enrollment in any other type of medical research judged not to be scientifically or medically compatible with this study
- if the participant, for any reason, requires treatment with another therapeutic agent that has been demonstrated to be effective for treatment of the study indication, discontinuation from the study occurs prior to introduction of the new agent

Discontinuation is expected to be uncommon.

At the time of discontinuing from the study, if possible, an early discontinuation visit should be conducted, as shown in the SoA. See the SoA (Section 1.3) for data to be collected at the time of study discontinuation and follow-up and for any further evaluations that need to be completed. The participant will be permanently discontinued both from the study intervention and from the study at that time.

If the participant withdraws consent for disclosure of future information, the sponsor may retain and continue to use any data collected before such a withdrawal of consent. If a participant withdraws from the study, he/she may request destruction of any samples taken and not tested, and the investigator must document this in the site study records.

7.2.1. Discontinuation of Inadvertently Enrolled Participants

If the sponsor or investigator identify a participant who did not meet enrollment criteria and was inadvertently enrolled, then the participant may continue to follow study procedures dependent on the cause for the incorrect enrollment. If the investigator and the sponsor CRP agree it is medically appropriate to continue, the investigator must obtain documented approval from the sponsor CRP to allow the inadvertently enrolled participant to continue in the study with or without treatment with investigational product (IP). The documented approval must contain the benefit/risk assessment and a robust clinical justification that continuing in the study will not jeopardize the participant's safety. All inadvertently enrolled participants will complete safety follow-up as outlined in Section 1.3 (SoA), Section 8.2 (Safety Assessments), and Section 8.3 (Adverse Events and Serious Adverse Events) of the protocol.

7.3. Lost to Follow-Up

A participant will be considered lost to follow-up if he or she repeatedly fails to return for scheduled visits and is unable to be contacted by the study site. Site personnel are expected to make diligent attempts to contact participants who fail to return for a scheduled visit or were otherwise unable to be followed up by the site.

Site personnel, or an independent third party, will attempt to collect the vital status of the participant within legal and ethical boundaries for all participants randomized, including those who did not get IP. Public sources may be searched for vital status information. If vital status is determined to be deceased, this will be documented and the participant will not be considered lost to follow-up.

Discontinuation of specific sites or of the study as a whole are handled as part of [Appendix 1](#).

8. Study Assessments and Procedures

- Study procedures and their timing are summarized in the SoA (Section 1.3). Protocol waivers or exemptions are not allowed.
- Immediate safety concerns should be discussed with the sponsor immediately upon occurrence or awareness to determine if the participant should continue or discontinue study intervention.
- Adherence to the study design requirements, including those specified in the SoA, is essential and required for study conduct.
- All screening evaluations must be completed and reviewed to confirm that potential participants meet all eligibility criteria. The investigator will maintain a screening log to record details of all participants screened and to confirm eligibility or record reasons for screening failure, as applicable.
- The specifications in this protocol for the timings of safety and sample collection are given as targets to be achieved within reasonable limits. Modifications may be made to the time points based upon emerging clinical information. The scheduled time points may be subject to minor alterations; however, the actual time has to be correctly recorded in the CRF. Failure or being late (that is, outside stipulated time allowances) to perform procedures or obtain samples due to legitimate clinical issues (for example, equipment technical problems, venous access difficulty, or participant defaulting or turning up late on an agreed scheduled procedure) will not be considered as protocol deviations, but the CRU will still be required to notify the sponsor in writing via a file note.
- [Appendix 2](#) lists the laboratory tests that will be performed for this study.
- Section 10.2.1 of [Appendix 2](#) provides a summary of the maximum number and volume of invasive samples, for all sampling, during the study.
- Unless otherwise stated in subsections below, all samples collected for specified laboratory tests will be destroyed within 60 days of receipt of confirmed test results. Certain samples may be retained for a longer period, if necessary, to comply with applicable laws, regulations, or laboratory certification standards.

8.1. Efficacy Assessments

Not applicable.

8.2. Safety Assessments

Planned time points for all safety assessments are provided in the SoA (Section 1.3).

8.2.1. Physical Examinations

- A complete physical examination will include, at a minimum, assessments of the cardiovascular, respiratory, GI, and neurological systems. Height and weight will also be measured and recorded at screening.
- A brief physical examination will include, at a minimum, assessments of the skin, lungs, cardiovascular system, and abdomen (liver and spleen).
- Investigators should pay special attention to clinical signs related to previous serious illnesses.

8.2.2. Vital Signs

- For each participant, vital sign measurements should be conducted according to the SoA (Section 1.3) and following the study-specific recommendations included in a Manual of Operations for the study. Vital sign measurements will be recorded before collecting any blood samples.
- Blood pressure and pulse rate should be measured after at least 5 minutes supine, and taken in triplicate.
- If orthostatic measurements are required, participants should be supine for at least 5 minutes and stand for at least 3 minutes.
- If the participant feels unable to stand, supine vital signs only will be recorded.
- Unscheduled orthostatic vital signs should be assessed, if possible, during any AE of dizziness or posture-induced symptoms. Additional vital signs may be measured during each study period if warranted.

8.2.3. Electrocardiograms

- Single, 12-lead ECGs will be obtained as outlined in the SoA (see Section 1.3) using an ECG machine that automatically calculates the heart rate and measures pulse rate, QRS, QT, and corrected QT intervals (QTc).
- For each participant, ECGs should be collected according to the SoA (Section 1.3) and the study-specific recommendations included in the Manual of Operations for the study.
- Any clinically significant findings from ECGs that result in a diagnosis, and that occur after the participant receives the first dose of the study intervention, should be reported to the sponsor or its designee as an AE via electronic case report form (eCRF)
- Electrocardiograms must be recorded before collecting any blood samples. Participants must be supine for approximately 5 to 10 minutes before ECG collection and remain supine but awake during ECG collection. Electrocardiograms may be obtained at additional times, when deemed clinically necessary. All ECGs recorded should be stored at the investigational site.

- Electrocardiograms will be interpreted by a qualified investigator (the physician or qualified designee) at the site as soon after the time of ECG collection as possible, and ideally while the participant is still present, to determine whether the participant meets entry criteria at the relevant visit(s) and for immediate participant management, should any clinically relevant findings be identified.

8.2.4. Clinical Safety Laboratory Assessments

- See [Appendix 2](#) for the list of clinical laboratory tests to be performed and the SoA (Section 1.3) for the timing and frequency.
- The investigator must review the laboratory report, document this review, and record any clinically relevant changes occurring during the study in the AE section of the CRF. The laboratory reports must be filed with the source documents. Clinically significant abnormal laboratory findings are those which are not associated with the underlying disease, unless judged by the investigator to be more severe than expected for the participant's condition.
- All laboratory tests with values considered clinically significantly abnormal during participation in the study, or within 28 days after the last dose of study intervention, should be repeated until the values return to normal or baseline or are no longer considered clinically significant by the investigator or medical monitor.
 - If such values do not return to normal/baseline within a period of time judged reasonable by the investigator, the etiology should be identified and the sponsor notified.
 - All protocol-required laboratory assessments, as defined in [Appendix 2](#), must be conducted in accordance with the laboratory manual and the SoA (Section 1.3).
 - If laboratory values from nonprotocol-specified laboratory assessments, performed at the institution's local laboratory, require a change in participant management or are considered clinically significant by the investigator (for example, SAE, AE, or dose modification), then the results must be recorded in the CRF.

8.2.5. Injection Site Reactions

- Injection site assessments using the ISR questionnaire and an exploratory tool (Scarletred) will be performed at times specified in the SoA (Section 1.3).
- Manifestations of a local ISR may include erythema, induration, pain, pruritus, and edema. Injection site findings will be captured on the eCRF.
- Injection site reactions, whether recorded as a result of the prespecified (or solicited) assessment or spontaneously reported reactions, will be recorded as AEs only if they qualify as severe AEs.

- If a spontaneous (or unsolicited) ISR is reported by a participant or investigator, the ISR CRF will be used to capture additional information about this reaction (for example, degree and area of erythema) at additional visits until resolution of the event.
- Injection site pain assessments are part of the solicited and spontaneous ISR assessments. All positive responses of pain will require an additional assessment using the Pain Visual Analog Scale (Pain VAS). The VAS will be performed at times specified in the SoA (Section 1.3). If there are 2 injections, timing will relate to the second injection. Pain measurements will be quantified using the 100-mm VAS pain score for all participants, regardless of whether they report ISP. The VAS is a well-validated tool (Williamson and Hoggart 2005) to assess ISP; it is presented as a 100-mm line anchored by verbal descriptors, usually “no pain” and “worst imaginable pain.” The participant will be asked to rate any pain at the injection site on a scale of 0 to 100 mm on the line immediately (within 1 minute) following the injection.
- In addition, the exploratory tool (Scarletred) will be used to acquire exploratory ISR data at each of the time points where the ISR data is being collected by administration of the ISR questionnaire. Failure to take this assessment at any of the indicated time points will not result in a protocol deviation.

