6.6. Dose Modification

If moderate or severe AEs are consistently observed across participants in a group or if unacceptable pharmacological effects, reasonably attributable to ramucirumab administration in the opinion of the investigator, are observed in more than 2 of the participants in a group, then no further participants will be dosed until a full safety review of the study has taken place. Relevant reporting and discussion with the Medical Monitor/Sponsor, relevant personnel, and the Institutional Review Boards (IRBs)/Independent Ethics Committees (IECs) will take place before resumption of dosing.

If the SAE occurs in 1 participant in a group, then dose escalation will be temporarily halted and no further participants will be dosed until a full safety review of the data has taken place. Relevant reporting and discussion with the Medical Monitor, relevant personnel, and the IRB/IEC will take place before resumption of dosing.

Refer to Section 10.3.5 of Appendix 3 for additional information about the sponsor's surveillance process for dose escalation and group expansion.

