8.3.1. Time Period and Frequency for Collecting AE and SAE Information

All SAEs will be collected from the signing of the ICF until participation in the study has ended.

All AEs will be collected from the signing of the ICF until participation in study has ended.

Adverse events that begin before the start of study intervention, but after signing of the ICF, will be recorded on the AE CRF.

Although all AEs after signing the ICF are recorded by the site in the CRF/electronic data entry, SAE reporting to sponsor begins after the participant has signed the ICF and has received the study intervention. However, if an SAE occurs after signing the ICF, but prior to receiving ramucirumab, it needs to be reported ONLY if it is considered reasonably possibly related to study procedures.

All SAEs will be recorded and reported to the sponsor or designee immediately, and under no circumstance should this exceed 24 hours, as indicated in [Appendix 3](#) (Section 10.3). The investigator will submit any updated SAE data to the sponsor within 24 hours of it being available.

Investigators are not obligated to actively seek AEs or SAEs after conclusion of the study participation. However, if the investigator learns of any SAE, including a death, at any time after a participant has been discharged from the study, and he/she considers the event to be reasonably related to the study intervention or study participation, the investigator must promptly notify the sponsor.

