10.3.2. Definition of SAE

If an event is not an AE per the definition above, then it cannot be an SAE even if serious conditions are met (for example, hospitalization for signs/symptoms of the disease under study, death due to progression of disease).

An SAE is defined as any untoward medical occurrence that, at any dose:

a. Results in death

b. Is life-threatening

The term ‘life-threatening’ in the definition of ‘serious’ refers to an event in which the participant was at risk of death at the time of the event. It does not refer to an event, which hypothetically might have caused death, if it were more severe.

c. Requires inpatient hospitalization or prolongation of existing hospitalization

- In general, hospitalization signifies that the participant has been admitted to the hospital for observation and/or treatment that would not have been appropriate in the physician’s office or outpatient setting. Complications that occur during hospitalization are AEs. If a complication prolongs hospitalization or fulfills any other serious criteria, the event is serious. When in doubt as to whether “hospitalization” occurred or was necessary, the AE should be considered serious.
- Hospitalization for elective treatment of a preexisting condition that did not worsen from baseline is not considered an AE.

d. Results in persistent disability/incapacity

- The term disability means a substantial disruption of a person’s ability to conduct normal life functions.
- This definition is not intended to include experiences of relatively minor medical significance such as uncomplicated headache, nausea, vomiting, diarrhea, influenza, and accidental trauma (for example, sprained ankle) which may interfere with or prevent everyday life functions but do not constitute a substantial disruption.

e. Is a congenital anomaly/birth defect

f. Other situations:

- Medical or scientific judgment should be exercised in deciding whether SAE reporting is

appropriate in other situations such as important medical events that may not be immediately life-threatening or result in death or hospitalization but may jeopardize the participant or may require medical or surgical intervention to prevent one of the other outcomes listed in the above definition. These events should usually be considered serious.

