10.3.3. Recording and Follow-Up of AEs and/or SAEs

AE and SAE Recording

- When an AE/SAE occurs, it is the responsibility of the investigator to review all documentation (for example, hospital progress notes, laboratory reports, and diagnostics reports) related to the event.
- The investigator will then record all relevant AE/SAE information on the CRF.
- It is **not** acceptable for the investigator to send photocopies of the participant's medical records to the sponsor or designee in lieu of completion of the AE/SAE CRF page.
- There may be instances when copies of medical records for certain cases are requested by the sponsor or designee. In this case, all participant identifiers, with the exception of the participant number, will be redacted on the copies of the medical records before submission to the sponsor or designee.
- The investigator will attempt to establish a diagnosis of the event based on signs, symptoms, and/or other clinical information. Whenever possible, the diagnosis (not the individual signs/symptoms) will be documented as the AE/SAE.

Assessment of Intensity

The investigator will make an assessment of intensity for each AE and SAE reported during the study and assign it to 1 of the following categories:

- Mild: An event that is easily tolerated by the participant, causing minimal discomfort and not interfering with everyday activities.
- Moderate: An event that causes sufficient discomfort and interferes with normal everyday activities.
- Severe: An event that prevents normal everyday activities. An AE that is assessed as severe should not be confused with an SAE. Severe is a category utilized for rating the intensity of an event; and both AEs and SAEs can be assessed as severe.
- An event is defined as 'serious' when it meets at least 1 of the predefined outcomes described in the definition of an SAE, NOT when it is rated as severe.
- The investigator will use CTCAE version 5.0 (NCI 2018) to assign AE severity grades.

Assessment of Causality

- The investigator is obligated to assess the relationship between study intervention and each occurrence of each AE/SAE.
- A “reasonable possibility” of a relationship conveys that there are facts, evidence, and/or arguments to suggest a causal relationship, rather than a relationship, cannot be ruled out.
- The investigator will use clinical judgment to determine the relationship.

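### Protocol 8.2.5 makes severity the only test for recording an injection site reaction as an AE, which contradicts the SAE rules for a reaction that is serious but not severe

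*Protocol*

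**What the plan says.** Protocol 8.2.5 covers both solicited and spontaneous ISRs and gives one rule for moving them to the AE record: they "will be recorded as AEs only if they qualify as severe AEs". All injection site findings still go on the eCRF, and SAP 9.4.8 and 9.4.9 list and summarize ISRs and injection site pain.

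Protocol 10.3.3 keeps intensity and seriousness apart. It warns that "An AE that is assessed as severe should not be confused with an SAE", and says an event is serious when it meets one of the outcomes "described in the definition of an SAE, NOT when it is rated as severe". Those outcomes are in 10.3.2. They include an event that "Requires inpatient hospitalization or prolongation of existing hospitalization", and an important medical event that "may jeopardize the participant or may require medical or surgical intervention to prevent one of the other outcomes listed in the above definition".

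On reporting, 8.3.1 states: "All SAEs will be recorded and reported to the sponsor or designee immediately, and under no circumstance should this exceed 24 hours". Section 10.3.4 repeats the 24-hour duty for any SAE and sends the notification through SAE forms. Neither section makes an exception for ISRs. Section 6.6 adds a stopping rule: "If the SAE occurs in 1 participant in a group, then dose escalation will be temporarily halted and no further participants will be dosed".

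**The concern.** The rule in 8.2.5 is exclusive, and its only criterion is intensity. A reaction of mild or moderate intensity can still meet a seriousness criterion. For that reaction, the one sentence written specifically about recording ISRs tells the site not to enter an AE, while the general safety sections tell it to record and report an SAE within a day. No text ranks the two instructions, and the SAP does not reconcile them.

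Two things depend on prompt recognition. SAE incidence is part of a primary endpoint (Protocol, Section 3), and a single SAE in a group stops dosing under 6.6. A table of ISRs produced at the end of the study does neither job: the 24-hour report and the halt act while participants are still being dosed.

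Keeping ordinary mild and moderate ISRs off the AE record is not the problem. They have their own capture and their own summaries.

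**Working it through.** No arithmetic decides this point, and the plan states no figure to reproduce. The check sets the sections side by side and follows one event through them: an ISR of moderate intensity that needs medical intervention to prevent a listed outcome.

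1. **Is it an AE?** By the definition in 10.3.1, yes. It is an untoward medical occurrence after study drug, and ISRs are not among the listed exclusions.
2. **Is it an SAE?** By 10.3.2, yes. That section makes SAE status depend on the AE definition just before it, not on whether an AE entry was made.
3. **Is it recorded as an AE?** By 8.2.5, no, because it is not severe. By 8.3.1, yes, because all AEs are collected and all SAEs are recorded and reported. Section 8.2.6 also asks for all AEs of every CTCAE grade. For this event a site cannot follow both.
4. **Is it reported as an SAE?** By 8.3.1 and 10.3.4, yes, within 24 hours and without exception. Section 8.2.5 is silent on SAE reporting.
5. **Does the halt apply?** By 6.6, yes. The trigger is that an SAE occurs, not that an AE page is filled in.

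Steps 1, 2, 4 and 5 agree with each other. Step 3 is where the contradiction lies.

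**How large is the affected set?** It is the set of ISRs that are serious but not severe. Section 10.3.3 defines severe as preventing normal everyday activities, so a local reaction that led to hospital admission would usually be severe already. Two kinds of event remain. One is a moderate reaction treated as an important medical event. The other is a moderate reaction that lengthens a stay: 4.1 lets the investigator keep a participant in the unit beyond Day 8, and 10.3.2 says that doubt about hospitalization is to be resolved as serious. The set is very small but not empty.

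**What would one event do?** Each group plans 7 participants on ramucirumab. If one of them had such an event and it were left out of the SAE count, that arm would show 0/7 instead of 1/7 = 14.3%. The 6.6 threshold is 1 participant, so a delay in recognizing that one event is a delay in the halt. This shows the effect of a single event. It does not estimate how often one would occur.

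**The case against.** The strongest reply is that the SAE system does not depend on 8.2.5. SAE status comes from 10.3.1 and 10.3.2, the reporting duty in 8.3.1 and 10.3.4 is unqualified, and 6.6 acts when an SAE occurs. A careful site would report the event. Systemic allergic or hypersensitivity reactions fall under 8.2.6.1, which calls for an AE record with no severity threshold, so 8.2.5 is left mainly with local reactions. All of this stands, and it limits the point.

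A reader might go further and infer that a serious, non-severe ISR is necessarily kept off the SAE record, and that the 6.6 halt is thereby defeated. The documents do not support that. The phrase "in lieu of completion of the AE/SAE CRF page" in 10.3.3 might suggest that a single form feeds both records, but it comes from a sentence barring photocopied medical records. It does not show that an SAE can be captured only through an AE entry. Section 10.3.4 describes separate SAE forms, and SAP 9.4.1 says SAEs are listed without naming a source dataset. Nor can one conclude that the ISR form lacks a seriousness item, because the form is not in the documents.

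A reader might also want a probability. The documents give no rate for serious, non-severe ISRs and none for a site preferring 8.2.5 over 8.3.1, so any figure would be invented.

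The reply does not make 8.2.5 correct. For this event its instruction is wrong and contradicts 8.3.1, and relying on sites to override it is weaker than stating the rule properly.

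**Conclusion.** Wrong as written, and minor. Section 8.2.5 omits seriousness, and for an ISR of mild or moderate intensity that meets a 10.3.2 criterion it contradicts 8.3.1 and 10.3.4. The SAE route and the 6.6 halt remain in force. The risk is one of conduct: a site following 8.2.5 literally could omit the AE entry, and the SAE report and the one-SAE halt could then be late.

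The conclusion rests on reading *only if* in its plain sense and on the protocol's own separation of severe from serious. It assumes no event rate. Nothing in the documents suggests that such an event has occurred.

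**What to change.** In Protocol 8.2.5, add the words *or serious* after *severe*, so that an ISR is recorded as an AE if it is severe or serious. Then add one sentence: *Any ISR meeting a 10.3.2 criterion is reported under 8.3.1 and 10.3.4 and counts for 6.6.*

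The cost is two words and one sentence in the next protocol amendment, with the usual IRB/IEC approval. No new data are collected, and ordinary mild and moderate ISRs are handled as now. The one downside is that a serious ISR will appear in both the AE and the ISR outputs, as a severe one already does.

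The correction does not require a SAP change, since SAP 9.4.1 already lists SAEs. Nor does it require a review of the ISR records from Groups 1 and 2, whose 2-week safety data have been reviewed (Protocol 4.3).
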